### **12.5 Safety and Tolerability Data**

Demographics will be tabulated and summarized. Medical and surgical history data at Screening will be listed, as will Physical Examination data (including height and weight) at Screening, and at subsequent visits. All characteristics at baseline such as age, weight, height and vital signs (resting heart rate, semi-supine systolic/diastolic blood pressure, respiratory rate and temperature) parameters will be tabulated and summarized.

All patients receiving at least one dose of IMG-7289 will be included in the safety analysis.

Laboratory values outside the laboratory normal ranges will be summarized and assessed for change from Day 0 and trends indicating a safety signal.

Treatment-emergent adverse events will be coded using the Medical Dictionary for Regulatory Activities (MedDRA) and summarized for the number of patients reporting the AE and the number of AEs reported. A by-patient AE data listing including (but not limited to) verbatim term, coded term, severity, and relationship to treatment will be provided.

Concomitant medications will be listed by patient and coded using the WHO drug dictionary. Medical history will be listed by patient.

Descriptive statistics (arithmetic mean, standard deviation (SD), sample size, CV (coefficient of variation), median, minimum, maximum, and number) will be calculated for quantitative safety data as well as for the differences to baseline, when appropriate. In addition, a shift table describing out of normal range shifts will be provided for clinical laboratory results and physical examination results. For safety and tolerability, missing data including those not obtained because of death will be the last value carried forward.

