- Changes in physical examinations, vital signs and laboratory values will also be evaluated and assessed from Screening/Baseline until End of Study (EoS)/End of Treatment (ET). Information on the timing of these assessments is presented in the schedule of assessment. **CCI**

CCI

- Pharmacokinetic (PK) parameters will be determined using serial blood sampling at specified time-points to determine PK effects of IMG-7289 (Phase 1/2a only). Non-compartmental methods of analysis will be used to determine PK parameters following oral dosing of patients. **CCI**

CCI

[figure not shown]
CCI

- Reduction in spleen volume will be assessed based on spleen volume measured by MRI (or CT scan where applicable) from Day 0, and spleen size measured by palpation from Baseline to each visit where the variables are measured.

CCI

[figure not shown]

IV. Study Design

A. Design Overview

This is a multi-center, open-label study evaluating the safety, tolerability, steady-state pharmacokinetics and pharmacodynamics of IMG-7289 administered orally once daily in patients with myelofibrosis (MF).

The therapeutic goal for the treatment of MF is to inhibit the activity of LSD1 in haematopoietic cells for only a fraction of the 24-hour dosing cycle sufficient to reduce platelets to a safe level while inhibiting to the greatest extent possible the production, by megakaryocytes, of cytokines and growth factors that drive bone marrow fibrogenesis and symptoms. Considerations for a safe and therapeutic starting dose included chronic toxicology studies, in conjunction with clinical experience of the patients who have received IMG-7289 to date in both IMG-7289-CTP-101 and -102. CCI

CCI

This study initiated as a Phase 1/2a study, assessing the safety of the starting dose, an 85-day duration of treatment, and the pharmacokinetic and pharmacodynamic effects of IMG-7289, with transition to a Phase 2b study including implementation of changes supported by the Phase 1/2a data.

This study consists of two treatment periods: The Initial Treatment Period (ITP), followed by the Additional Treatment Period (ATP); the ATP is iterative, and allows patients to continue treatment if they derive clinical benefit (defined as not meeting progressive disease criteria as per protocol Section **Erreur ! Source du renvoi introuvable.**) and safety tolerating IMG-7289 as determined by the Principal Investigator

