The analyses described in this plan are considered *a priori*, in that they have been defined prior to database lock. If any post-hoc analyses are performed, they will be defined and reported in the CSR.

All analyses will be performed using SAS statistical analysis software version 9.4 or higher of SAS for Windows [SAS Institute Inc; Cary, NC, USA]).

A. Data Sources

All data are collected *via* electronic case report forms (eCRFs) through remote data entry. Section 13.6 of the protocol describes data quality assurance.

B. Definition of Baseline

For analysis purposes, baseline is defined as the last assessment prior to the first dose of study drug. Day 0 is the first day a patient receives study drug. For most measurements, baseline assessments will be taken pre-dose on Initial Treatment Period ITP Day 0. If pre-dose assessments on Day 0 are not available, the most recent prior assessment closest to Day 0 may be substituted in some cases, and unless otherwise specified.

C. Missing Data

For safety and tolerability, missing data, including those not obtained because of death, will be the last value carried forward.

If CTCAE Grade is missing, the event is assumed to be ‘Severe’ (grade 3). If AE relatedness is missing, the event is assumed to be ‘possibly’ related.

When relevant, sections below will address how missing data will be handled for the particular analyses. Otherwise, missing data will not be replaced with imputed values.

D. Display and Imputation Methods for Missing Dates

Every effort will be made to query missing dates. However, partial dates are allowed on the eCRF for Adverse Event (AE) onset and resolution dates (only month and year are required), Concomitant Medication (CM) start and stop dates (only year is required), and Prior and Concurrent Cancer Chemotherapy (PCTHX) start and stop dates (only year is required).

Per protocol, Adverse Events (AEs) are captured in the eCRF commencing with the first dose of IMG-7289 through to the End of Study Visit (scheduled for approximately 28 days post last IMG-7289 dose). For records with missing AE onset day, the following procedure will be employed for use in determining whether the AE is treatment-emergent:

- AE onset dates with missing day will be assumed to occur on the first day of the non-missing month, except for AEs occurring in the first month of dosing, in which case the date will be the first day of dosing.

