Additionally, if for some reason the start date of an AE is partially or completely missing and the end date of the AE does not indicate that the AE occurred prior to the first dose of IMG-7289, then the determination of treatment-emergent status will be based on the following:

- If the start date is completely missing, then the AE is treatment-emergent.
- If the start year is the same as the year of the first dose of study drug and the start month is the same or after the month of the first dose of study drug, then the AE is treatment-emergent.
- If the start year is after the year of the first dose of study drug, then the AE is treatment emergent.

For records with a missing CM or PCTHX start and/or stop day or month, the following procedure will be employed for use in determining whether the therapy (i.e., medication or chemotherapy) is prior or concomitant/concurrent:

- Therapy start dates with a missing day and non-missing month will be assumed to occur on the *first* day of the non-missing month, except for therapies occurring in the first month of dosing, in which case the date will be the first day of dosing.

- Therapy start dates with a missing day and month will be assumed to occur on the *first* day of the non-missing year (i.e., January 1), except for medications occurring in the first year of dosing, in which case the date will be the first day of dosing.
- Therapies that are not marked as ongoing, and have a stop date with a missing day and non-missing month will be assumed to occur on the *last* day of the non-missing month.
- Therapies that are not marked as ongoing, and have a stop date with a missing day and month will be assumed to occur on the *last* day of the non-missing year (i.e. December 31).

For the listings, AE, CM and PCTHX dates will be listed as collected in the eCRF.

All other data will be reported as they are collected. No imputation methods will be used to replace missing data unless otherwise stated in this document.

Partial transfusion start dates are not permitted, and thus assumptions should not be needed to determine if the transfusion was prior to the first dose of IMG-7289.

E. Multiple Study Centers

There will be no adjustment for multiple study centers in the analysis.

F. Covariate Adjustment in Primary Analysis

There will be no adjustment in the analysis for covariates.

G. Sample Size Reassessment

No sample size reassessment is planned for this study.

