H. Interim Analyses and Data Safety Monitoring Committee (DSMC)

No formal interim analysis is planned for this study.

The DSMC reviews safety parameters and pharmacodynamic markers to draw conclusions around the safety and pharmacodynamic effect of IMG-7289. The DSMC responsibilities will remain in effect until study has ended.

The DSMC/SAB also reviews patient dose titrations and may recommend adjustments. At the original starting dose of 0.25 mg/kg/day, two sentinel patients were dosed for 7 days of treatment before initiating enrollment on a rolling basis. Data from the first sentinel patient was reviewed by the DSMC prior to dosing the second sentinel patient. The DSMC/SAB convened within 4 days post-completion of 7 days of treatment for each of the sentinel patients at the original D_s and determined that it was safe for each sentinel patient to continue dosing, and that it was safe for additional patients to begin treatment with IMG-7289.

Additionally, the DSMC convened post-completion of 7 days of treatment of the required three patients at the new starting dose of 0.5 mg/kg/day and determined:

the safety of the new 0.5 mg/kg/day starting dose, and the ITP Day 3 (mid-week) visit could be removed from the visit schedule.

The DSMC is scheduled to meet at least monthly during Phase 1/2a and quarterly during Phase 2b.

I. Multiple Comparisons

No control for the effect of multiple comparisons is planned.

J. Application of Visit Windows

In general, summaries will present the visits that are expected for each dose/cohort. Visits will be represented by treatment period (ITP or ATP) and day within period; for subjects that experience more than one ATP, each ATP will be treated separately (e.g. ATP1, ATP2). If a visit that is presented on a particular page is expected for some dose/cohorts but not others, then the summary will indicate “n/a” for the visits that are not expected for that particular dose/cohort.

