Sites are intended to document on the AE eCRF those events with an onset date on or after the date on which IMG-7289 was first dispensed, and within 28 days of last IMG-7289 treatment; therefore, all reported AEs are expected to be treatment-emergent. However, if eCRF completion guidelines change, or are not followed adequately, treatment-emergent events will be identified programmatically per the above definition, using imputed start date.

CCI

C. Clinical Laboratory Results

The following laboratory tests will be conducted:

- Complete blood counts (CBC) and differential
- Coagulation
- Chemistry panel including LFTs (AST, ALT, total bilirubin and alkaline phosphatase (ALP)) gamma glutamyltransferase (GGT), albumin , C-reactive protein), lactate dehydrogenase (LDH), uric acid. *Note that C-reactive protein was added starting with amendment 5.*
- Urinalysis with microscopy

Laboratory values will be listed and summarized at each assessment. Numerical laboratory results will be summarized for the actual values, change from baseline (CFB), and percentage CFB by visit; and for the maximum and minimum change from baseline. P-value for test to assess maximum and minimum change from baseline within each cohort will be calculated using paired t-test.

Shift tables for laboratory values with respect to normal range (low, normal, high) and CTCAE toxicity grade, compared to baseline, will be summarized by visit. Overall laboratory result shift from baseline (Normal, Abnormal clinically significant (CS), and Abnormal non-clinically significant (NSC)) will be summarized.

D. Vital Signs

Vital sign assessments will be summarized for the actual values, change from baseline, and percentage change from baseline by visit; and for the maximum and minimum change from baseline. P-value for test to assess maximum and minimum change from baseline within each cohort will be calculated using paired t-test.

E. Physical Examination

Physical exam data will be listed. Note that for Phase 2b patients, a limited version of physical exam data is collected.

F. Prior and Concomitant Medications

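### The carry-forward rule for safety data expressly covers death and has no stop point, so by-visit laboratory and vital-sign tables would include patients who have died; its reach to patients who stop treatment is unclear

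*SAP*

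**What the plan says.** SAP VI.C, Missing Data: "For safety and tolerability, missing data, including those not obtained because of death, will be the last value carried forward". Protocol 12.5 has the matching sentence: "For safety and tolerability, missing data including those not obtained because of death will be the last value carried forward". Neither names an end to the carrying, whether death, last dose, a follow-up visit or the close of a treatment period.

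Two general sentences in the SAP point the other way. VI.C ends with "Otherwise, missing data will not be replaced with imputed values", and VI.D has "No imputation methods will be used to replace missing data unless otherwise stated in this document".

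The tables concerned are in SAP IX. For laboratory data, IX.C summarises numerical results by visit and adds: "Shift tables for laboratory values with respect to normal range (low, normal, high) and CTCAE toxicity grade, compared to baseline, will be summarized by visit". For vital signs, IX.D says: "Vital sign assessments will be summarized for the actual values, change from baseline, and percentage change from baseline by visit". On rows, VI.J says that "summaries will present the visits that are expected for each dose/cohort". The only analysis population is the Safety population, meaning everyone dosed (VI.K), and sample size is one of the reported statistics (VI.M).

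On the period of assessment, SAP III.A says that changes in physical examinations, vital signs and laboratory values are "evaluated and assessed from Screening/Baseline until End of Study", and the sentence goes on to give EoS/ET as the end. Protocol 12.4.1 also ends at EoS/ET.

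**The concern.** Safety is a primary objective, and changes in laboratory values and vital signs are listed among the primary endpoints. The by-visit tables are where a reader looks to see how these measures move over time and how many patients support each row. Protocol 12.5 itself wants laboratory values examined for trends that could signal harm.

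A value repeated after death is not a measurement. It holds the visit n up when patients have been lost, places a dead patient in a CTCAE grade at later visits, and blends a frozen value into the mean of those still observed. The direction of the distortion is not fixed. Values taken shortly before death may be poor. If off-drug values were also carried, platelet counts could be high, because Protocol 6.5 (item 4) and 8.2.1 describe a rebound above baseline once the drug is stopped.

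**Working it through.** **1. Does other text switch the rule off?** No. The VI.C sentence applies only to what the specific rules leave over, and the VI.D sentence excepts anything stated elsewhere in the SAP. Both yield to the safety rule. IX.C and IX.D state no rule of their own.

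**2. Are values after death really within the rule?** Yes. Data not obtained because of death are, by their nature, those due after it. If the rule stopped at death, that clause would cover nothing.

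**3. Rows filled per death (Phase 2b ITP).** Protocol 5.1.1 and 9.3 give the haematology and vital-sign visits: Days 7, 14, 21, 28, 35, 42, 49, 56, 70, 84, 98, 112, 140 and 168, which makes 14 post-baseline rows. The Protocol Synopsis puts biochemistry and coagulation on Days 28, 56, 84, 112, 140 and 168, which makes 6. Rows filled = scheduled visits after the last one attended.

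| Last visit before death | Haematology and vital signs: later visits | Rows filled | Biochemistry and coagulation: rows filled |
|---|---|---|---|
| Day 28 | 35, 42, 49, 56, 70, 84, 98, 112, 140, 168 | 10 | 5 |
| Day 56 | 70, 84, 98, 112, 140, 168 | 6 | 4 |
| Day 84 | 98, 112, 140, 168 | 4 | 3 |
| Day 112 | 140, 168 | 2 | 2 |

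These counts use the visit labels in the eCRF, take the rule as having no stop, and leave out rows of the Additional Treatment Period (ATP).

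**4. Effect on one row.** With m patients observed and d carried, the table reports n = m + d instead of m. The mean moves by d/(m + d) times the difference between the carried mean and the observed mean. The documents give neither d nor that difference, so no figure can be put on it.

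**5. What is not affected.**
- Adverse event tables count patients with events and do not run by visit.
- Listings show recorded data.
- The laboratory and vital-sign p-values are for maximum and minimum change. Repeating a value already in a patient's series cannot alter its maximum or minimum, and a small simulation agreed. The exception is a patient with no post-baseline value, for whom a carried baseline would add a change of zero.
- Spleen measurements fall outside a rule worded for safety and tolerability.

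**6. Patients who stop treatment but are alive.** The passages pull in two directions.
- Towards carrying: the rule has no stop point, VI.J sets rows by cohort and not by who is still on treatment, and the population is everyone dosed.
- Against carrying: SAP III.A and Protocol 12.4.1 end the assessment at EoS/ET, and SAP IV.A moves patients who stop to EoT, pre-EoS and EoS visits. Later treatment-period visits may then simply not be due, and so not missing.

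The two documents do not even use ET alike: the SAP expands it as End of Treatment, while Protocol 9.6.3 uses it for early termination. The text does not settle the question.

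**The case against.** The strongest case against is that carrying forward covers only visits still due. The EoS/ET limit defines the period of safety assessment, and a patient who leaves treatment moves to a follow-up schedule, so later ITP rows are not missing for that patient. For living patients who stop, this is a fair reading and it stands. It does not rescue the rule for deaths. No visit is due after death, yet the rule names those data and carries them. The EoS/ET limit might shorten that carrying, but the rule does not say so.

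A reader might go further and infer that everyone who stops early is certainly carried, and then size the problem from the 75 planned patients and the minimum of 45 completers in SAP IV.C, which leaves 75 − 45 = 30 non-completers. The documents do not support this. The 45 is a required minimum and not a forecast, completion also requires the scan, the split of completers by phase is not given, and the sum treats every non-completer as carried. Likewise, rebound platelet values would fill later ITP rows only if follow-up values were eligible to be carried into them, which the SAP does not say.

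It is also true that the study has a single arm, that the tables are descriptive, and that disposition and exposure outputs (SAP VII.B and IX.A) help show who remained on treatment. This limits the harm but does not correct a wrong n or mean. Text beside the safety endpoints is blacked out and the table shells are a separate document. A limit could stand there, but none is visible.

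**Conclusion.** The point holds for deaths on the plain wording. By-visit laboratory and vital-sign summaries, and by-visit laboratory shift tables, would include imputed values for patients who have died, with an inflated visit n. For patients who stop treatment alive, the plan is ambiguous. If they are carried, later rows would show patients no longer on drug, possibly with rebound values.

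The total size cannot be derived, because no death or dropout rate is given. Per death in the Phase 2b ITP it is 10, 6, 4 or 2 haematology and vital-sign rows after Day 28, 56, 84 or 112, on the assumptions in step 3. The direction of bias is unknown. No planned by-visit test on these data is affected. The sentence should be corrected before database lock, as a repair to descriptive safety tables and not as a threat to the study's conclusions.

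**What to change.** Replace the carry-forward sentence in SAP VI.C with:

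> Laboratory and vital-sign data are summarised by visit on observed values with the number of patients observed; no value is imputed after death, treatment discontinuation or end of observation. EoT/ET, pre-EoS and EoS assessments are shown as follow-up rows and are not placed in treatment-period rows, including when visit windowing (VI.J) is applied, except where the last scheduled visit of a treatment period (Phase 1/2a or Phase 2b) serves as EoT, when it is counted once as that visit.

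The exception is needed because Protocol 9.6.1 lets the Day 168 visit stand in for EoT. Naming both phases covers the 85-day periods of Phase 1/2a. The reference to windowing is needed because VI.J allows values to be slotted by study day, which could otherwise put follow-up values into treatment rows.

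Align Protocol 12.5. Protocol 12.1 lets the SAP modify the protocol's plans but asks for an amendment when a primary endpoint's analysis changes in a major way. Laboratory and vital-sign changes are primary endpoints, so the sponsor should decide and record whether this change is major.

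The cost is one SAP sentence, the removal of carry-forward programming for these tables, and possibly an amendment. The visit n will fall over time, which reflects the data actually held.

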## 11.2 Adverse Events

The Investigator is responsible for monitoring the safety of patients who have enrolled in the study and for accurately documenting and reporting information as described in this section. Patients will be instructed to report to the Investigator any AE that they experience. Investigators will ask about the occurrence of AEs at each visit. Investigators are required to document all AEs occurring during the clinical study, commencing with the first dose of IMG-7289 through to the End of Study Visit (scheduled at 28 days post last IMG-7289 dose). Adverse event recording will continue for patients who discontinue study treatment early but remain in follow-up, until their End of Treatment, Pre-End of Study and End of Study Visits have been completed.

Note: Any medical event which occurs from the time of Informed Consent but prior to dosing with IMG-7289 must still be documented in the patient's medical notes and will be recorded on the appropriate medical history eCRF pages.

**Note:** In the UK, serious AEs (SAEs) will be recorded from time of consent through the EoS or until the Investigator and Imago BioSciences determine that follow-up is no longer necessary.

Adverse events will be recorded on designated eCRF pages. Each AE is to be characterised (i.e., verbatim term) and information provided regarding its seriousness, start and stop dates, intensity, outcome, and causal relationship with the study drug.

An AE is any undesirable physical, psychological or behavioral effect experienced by a patient during participation in an investigational study, in conjunction with the use of the drug or biologic, whether or not product-related. This includes any untoward signs or symptoms experienced by the patient from the time of first dose with IMG-7289 until completion of the study.

Adverse events may include, but are not limited to:

- Subjective or objective symptoms spontaneously offered by the patient and/or observed by the Investigator or medical staff
- Findings at physical examinations
- Laboratory abnormalities of clinical significance

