### 11.2.1 Adverse Event Intensity

Adverse event intensity will be evaluated using the National Cancer Institute (NCI) Common Terminology Criteria for Adverse Events (CTCAE) version 4.03, published 14 June 2010. For AEs not included in the NCI CTCAE, the Investigator will be required to assess the intensity of the adverse drug/biologic experience using the following categories and associated guidelines:

Grade	Guideline
1	Mild; asymptomatic or mild symptoms; clinical or diagnostic observations only; intervention not indicated
2	Moderate; minimal, local or noninvasive intervention indicated; limiting age-appropriate instrumental ADL*
3	Severe or medically significant but not immediately life-threatening; hospitalization or prolongation of hospitalization indicated; disabling; limiting self-care ADL**
4	Life-threatening consequences; urgent intervention indicated
5	Death related to AE

Note 1: A semi-colon indicates 'or' within the description of the grade.

Note 2: Activities of Daily Living (ADL)

\*Instrumental ADL refer to preparing meals, shopping for groceries or clothes, using the telephone, managing money, etc.

\*\*Self-care ADL refer to bathing, dressing and undressing, feeding self, using the toilet, taking medications, and not bedridden.

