The safety and tolerability of IMG-7289 will be assessed by the analysis of adverse events (AEs), as well as changes in physical examinations, vital signs, and laboratory values as detailed below, using the Safety Population.

A. Exposure

The summary will be presented by disease type (PMF, PPV-MF, and PET-MF) within the starting dose category and include the following:

The summary by patients:

- Summary of patient weekly IMG-7289 dose during initial treatment phase

All exposure data will also be listed by starting dose category, disease type (PMF, PPV-MF, and PET-MF) and patient.

B. Adverse Events

The AEs reported on the eCRFs will be coded using the latest version of MedDRA available to the sponsor at the time of study initiation (up-versioning will not occur), associating lower-level terms with preferred terms and system organ classes (SOC) by the primary hierarchy. The tables will display counts and percentages of patients who reported at least one AE in each system organ class represented in the AE data. Within each system organ class, the tables will

display the counts and percentages of patients reporting at least one AE, as designated by the preferred terms.

In the summary, if a causal relationship is considered probable, possible, or definite by the Investigator, the AE is considered to be “related”; while, if a causal relationship is considered remote/unlikely or unrelated, the AE is considered “unrelated”.

[figure not shown]
Severity of AEs will be reported using the NCI CTCAE grades (v4.03): Grade 1 - Mild, Grade 2 - Moderate, Grade 3 - Severe, Grade 4 - Life-Threatening, and Grade 5 - Fatal.

In any given category (e.g., SOC or preferred term) a patient will be counted only once. If a patient has the same AE on multiple occasions, only the highest toxicity grade will be used. Similarly, only the most related event will be used. For summaries of related events by toxicity grade, if a patient has the same AE with both “related” and “unrelated”, only the highest toxicity grade of the related event will be used. Percentages will be based on the number of patients in the subgroup of patients being tabulated and not the number of events. Summaries that are displayed by system organ class and preferred terms will be ordered by descending order of incidence of system organ class and preferred term within each system organ class.

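### The Grade 3 default for adverse events with a missing CTCAE grade would put an ungraded fatal event in the Grade 3 row, against its own outcome field

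*SAP*

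**What the plan says.** SAP VI.C (Missing Data) sets the default for an ungraded AE: "If CTCAE Grade is missing, the event is assumed to be" severe, which it equates with Grade 3. The next sentence does the same for causality: "If AE relatedness is missing, the event is assumed to be" possibly related. Neither sentence refers to any other field on the AE record.

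The same section opens with a general rule for safety data: "For safety and tolerability, missing data, including those not obtained because of death, will be the last value carried forward". It also leaves room for exceptions: "When relevant, sections below will address how missing data will be handled for the particular analyses".

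SAP IX.B (Adverse Events) reports severity on CTCAE v4.03, ending with "Grade 3 - Severe, Grade 4 - Life-Threatening, and Grade 5 - Fatal". A patient with repeated episodes of the same AE is counted once, at the highest grade. The section mentions summaries of related events by toxicity grade. Its visible text gives no other rule for a missing grade.

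Protocol 11.2 requires each AE to be characterised, with "information provided regarding its seriousness, start and stop dates, intensity, outcome, and causal relationship with the study drug". Intensity, outcome and seriousness are therefore separate items. The fallback scale in protocol 11.2.1 describes Grade 4 as "Life-threatening consequences; urgent intervention indicated" and reserves Grade 5 for death, but it applies only to AEs that CTCAE does not cover.

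**The concern.** A default for missing grades is normally meant to be cautious, and the companion default of possibly related suggests that this one is too. Grade 3 is cautious for an ungraded event that was really Grade 1 or 2. For an ungraded event that was really Grade 4 or 5, it errs in the favourable direction.

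A fatal outcome is the clearest case. The grade is missing, but the information that fixes it is not: the outcome field already says what the grade must be on the scale in SAP IX.B. The rule replaces known information with a lower value.

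Safety and tolerability, assessed through AEs, is a primary endpoint (protocol 12.4.1, SAP III.A). Summaries are split by starting dose and by disease type within starting dose (SAP VI.L), so columns are small and a single patient can decide whether a Grade 5 row is empty. A table with no Grade 5 event beside a listing that shows a fatal outcome would leave the report contradicting itself about a death.

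**Working it through.** The plan states no figure on this point, so there is nothing to reproduce. The check applies the rule to records and then sizes one misplaced patient.

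**Inputs**
- Rule: missing grade becomes Grade 3, unconditionally (SAP VI.C).
- Scale: Grades 1 to 5, with 4 life-threatening and 5 fatal (SAP IX.B).
- Other fields available: outcome and seriousness for every AE (protocol 11.2).
- Denominators: about 75 treated patients planned, of whom 18 were treated in Phase 1/2a (SAP IV.C).
- Number of ungraded fatal or life-threatening AEs: not given. One to three, in separate patients, is assumed for illustration.

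**Step 1. Can another visible rule rescue the grade?** The carry-forward rule does not yield Grade 4 or 5 for an AE that has no grade. The highest-grade rule in IX.B helps only if the same patient has another record of the same AE graded 4 or 5. The relatedness default adds a further effect: IX.B treats possible as related, so a fatal AE missing both items would be tabulated as a related Grade 3 event.

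**Step 2. Six invented records.** The alternative rule is Grade 5 if fatal, Grade 4 if life-threatening, otherwise Grade 3.

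| True grade | Recorded | SAP rule | Alternative |
|---|---|---|---|
| 5 | missing | 3 | 5 |
| 4 | missing | 3 | 4 |
| 4 | 4 | 4 | 4 |
| 3 | 3 | 3 | 3 |
| 2 | 2 | 2 | 2 |
| 1 | missing | 3 | 3 |

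SAP rule: Grade 2 = 1, Grade 3 = 4, Grade 4 = 1, Grade 5 = 0. Alternative: Grade 2 = 1, Grade 3 = 2, Grade 4 = 2, Grade 5 = 1. Grades 4 and 5 together total 1 under the SAP rule and 3 under the alternative. Grade 3 or higher is 5 under both (4 + 1 + 0 and 2 + 2 + 1).

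**Step 3. Size of one to three misplaced patients.** Percentage = x/n, with exact (Clopper-Pearson) 95% limits.

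| Patients in the Grade 5 row | n = 75 | n = 18 |
|---|---|---|
| 0 (as the SAP rule would show) | 0% (0 to 4.8) | 0% (0 to 18.5) |
| 1 | 1.3% (0.03 to 7.2) | 5.6% (0.1 to 27.3) |
| 2 | 2.7% (0.3 to 9.3) | 11.1% (1.4 to 34.7) |
| 3 | 4.0% (0.8 to 11.3) | 16.7% (3.6 to 41.4) |

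These percentages show how much one patient weighs in each column. They do not estimate how often the rule will be used.

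**The case against.** The strongest reply is that the trigger will hardly ever occur. Protocol 11.2 requires intensity for every AE. Protocol 11.2.4 requires serious events to be reported within 24 hours and updated, with immediate sponsor contact for fatal and life-threatening ones. Under protocol 14.4, monitors compare the case report forms with source, and the investigator signs once queries are resolved. The events at issue are the most closely followed in the trial. This stands as an argument about frequency. It does not make the rule right when it is used, and the SAP wrote the rule because it allows for missing grades.

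Second, the event is misplaced by grade, not lost. It still counts in any-grade and Grade 3-or-higher totals, and another record of the same AE at a higher grade would keep the patient in the higher row. This stands in full. A reader might infer that such a death disappears from the safety tables, and the documents do not support that.

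Third, part of SAP IX.B is redacted. It may list separate tables of deaths or serious AEs, or refine the rule, and VI.C allows for later refinement. The only by-grade summaries that the visible text names are those of related events. This is a real limit on what can be concluded.

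Fourth, the life-threatening half is weaker than the fatal half. The seriousness criterion in protocol 11.2.3 is the reporter's judgement of immediate risk of death, which is a separate assessment from a CTCAE grade. Protocol 11.2 shows that seriousness is recorded, but not that the specific criterion sits on the AE page; it may be only on the SAE Report Form. Mapping it to Grade 4 is a reasonable assumption, not a certainty.

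A reader might also infer that the rule could misclassify a dose-limiting toxicity, since one criterion refers to Grade 4 or 5 events. The documents do not support this. Under the synopsis definition, the event must occur through Day 7 and be judged related by the investigator, and the Medical Monitor and investigator decide what follows. Nothing visible derives these toxicities from grades imputed at analysis. Nor do the supplied texts mention SAE narratives, so no conflict with narratives can be claimed.

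**Conclusion.** The point holds in a limited form. As written, SAP VI.C assigns Grade 3 to an ungraded AE even when its recorded outcome is fatal, so that a by-grade summary would contradict the record. For an ungraded life-threatening AE, the grade would probably be too low as well. The rule is therefore not a worst-case imputation, although it does overstate ungraded Grade 1 and 2 events.

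The likely effect is small. One affected patient moves the Grade 5 row from 0/75 to 1/75 (1.3 percentage points), or from 0/18 to 1/18 (5.6 points) in Phase 1/2a. The conclusion assumes that at least one fatal or life-threatening AE still has no grade at database lock, that no other record of the same AE in that patient carries the higher grade, and that no redacted text overrides the rule. It is a desirable correction and does not put the trial's safety conclusions in doubt.

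**What to change.** Replace the missing-grade sentence in SAP VI.C with wording such as this:

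> If CTCAE grade is still missing after query: Grade 5 if the AE outcome is fatal; Grade 4 if the event is recorded as serious because life-threatening (AE eCRF or SAE Report Form); otherwise Grade 3. Imputed grades will be flagged in the listing.

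A table footnote giving the number of imputed grades would help readers. If the unredacted AE section already contains such a rule, a cross-reference from VI.C is enough.

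The cost is one SAP sentence and a few lines of programming. The Grade 5 branch needs only the outcome field, which is already collected. The Grade 4 branch may need a link to the SAE Report Form if the criterion is not on the AE page. No new patients, visits or assessments are needed. The change should be made before database lock.
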